1.2. Revision history

Non applicable.

1.3. How is the trial registered?

The trial is registered in the EU Clinical Trials Register (https://www.clinicaltrialsregister.eu/ctr-search/trial/2017-001438-25/NL)

1.4. What is the planned period of observation?

The expected date of the inclusion of the first patient is 31-MAY-2021.

The expected data of the completion of follow-up for the last patient is 31-MAY-2025.

Section 2. Introduction.

2.1. What is the background and rationale for the study?

Vanishing white matter (VWM) is a devastating leukodystrophy (genetic brain white matter disorder) caused by recessive mutations in the genes EIF2B1-5, encoding the 5 subunits of eukaryotic translation initiation factor 2B, eIF2B¹⁻⁴. In VWM, variants in the genes EIF2B1-5 decrease eIF2B activity and thereby constitutively activate the downstream integrated stress response (ISR)^{5, 6}.

Recently, guanabenz has been shown to impact the ISR and currently is the only registered drug with a known effect on the ISR. Guanabenz is an a2-adrenergic antihypertensive drug with proven safety in adults and children above 12 years of age⁷. Guanabenz binds to and inhibits protein phosphatase 1 (PPP1R15A), also known as GADD34⁸. GADD34 constitutes a feedback loop in the ISR. Modulation of GADD34 has shown beneficial effects in nonclinical models of several human diseases, in which the ISR is activated, such as amyotrophic lateral sclerosis^{9, 10}. The ameliorating effect of guanabenz that is anticipated on VWM has been substantiated in a mutant VWM mouse model representative for the human disease¹¹.

The aim of the guanabenz trial is to evaluate the safety, tolerability and efficacy of guanabenz in young children with VWM. For further details on the background and rationale of this study see pages 33 to 39 of the protocol.

2.2. What are the objectives of the study?

- The primary safety objective is to evaluate the safety and tolerability profile of guanabenz in pediatric patients with VWM.
- The primary efficacy objective is to evaluate how disability in terms of ambulation change over time in patients with VWM receiving guanabenz as compared to historical controls.
- The secondary objectives are
 - to evaluate the PK profile of guanabenz in patients with VWM
 - to evaluate overall survival in patients with VWM receiving guanabenz as compared to historical controls
 - to evaluate how quantitative MRI parameters relevant to brain white matter integrity change over time in patients with VWM receiving guanabenz.
- Exploratory objectives are
 - to perform exploratory PK-covariate and PK/PD analyses.
 - to perform exploratory biomarker analyses in blood and CSF.
 - To perform a Health Technology Assessment (HTA) concerning the use of guanabenz.

For further details see pages 40 of the protocol.

Section 3. Study Methods.

3.1. What is the study design?

This is an open-label, non-randomized study with a historical control group. All patients enrolled will receive guanabenz at their highest tolerated dose, with a target dose of 2 mg/kg/day, a minimum dose of 1 mg/kg/day, and a maximum dose of 10 mg/kg/day. Guanabenz will be administered as oral capsules once daily before bedtime and in addition to the patient's usual standard of care. The control group consists of historical VWM patients collected from an international longitudinal VWM registry with data collection over 20 years, investigating the natural disease course of VWM.

For more details see pages 41 to 50 of the protocol.

3.2. Will randomization be performed in this study?

No randomization is performed in this study.

3.3. How was the sample size calculated?

The planned sample size for this study (N=20 patients minimum, N=40 patients maximum) is not based on formal hypothesis testing considerations. Considering the low incidence of VWM, N=20-40 is the maximum number that realistically can be achieved over a period of 2-3 years. The planned sample size is deemed sufficient to provide preliminary assessments of safety and tolerability and to allow assessments of PK and major beneficial effects, such as major clinical improvement and any improvement of the brain MRI parameters.

A sample size of 20 patients is deemed necessary to obtain reliable estimates of clinical outcomes and their standard deviation. This information can be used to inform the design of future studies.

The following is an example for a power calculation based on the sample size, and the power might increase based on a 1:1 matching ratio. In the population with onset ≤6 years and eligible for study participation, the proportion of patients who with standard care will be alive and be able to walk without support after 2 years is estimated to be between 50% and 70%. Considering type I error equal to 0.1 and a McNemar test statistic, with 30 patients included within 3 years and 30 historical controls, the study has 80% power to declare guanabenz effective, if the proportion able to walk without support after 2 years increases from 50% to 80.1%, from 60% to 87.8%, or from 70% to 93.5%. With 40 patients included in 2 years and 40 historical controls, the study has 80% power to declare guanabenz effective, if the proportion able to walk without support after 2 years increases from 50% to 75.5%, from 60% to 83.3%, or from 70% to 90.1%. If the data are correlated, the power will increase.

This refers to page 53 of the research protocol.

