3.6. When will the final statistical analysis of the study data be performed?

The statistical analysis of the primary and secondary endpoints assessed during the hospital stay will be conducted after the last patient has been discharged and the database has been closed (scheduled for July 16, 2025). This will occur approximately one year after the final participants were enrolled, as inclusion ended on May 31, 2024. The current estimate is that these statistical analyses will be performed in August and September 2025.

3.7. At which time points are the outcomes measured and which "windows" are allowed?

The time points of the visits are presented in Table 3 on page 71 of the protocol. As stated on page 71, all visits have a visit window of 14 days before and after the nominal time points, except for visits M0, M12, M24, M36, M48, which have a visit window of 28 days before and after the nominal time points. As indicated on page 71, the end of study visit has to be in the last 6 months before the end of study on May 31, 2025.

Section 4. Statistical Principles.

4.1. Which level or levels of statistical significance will be used in the study?

Primary and secondary efficacy outcomes will be considered significantly different between guanabenz treated participants and historical controls if the one-sided p-values are less than 0.05.

4.2. Will the analysis adjust for multiplicity of statistical testing to ensure control of type I error rate?

As there is one primary efficacy endpoint (loss of ambulation), the analysis will not adjust for multiplicity of statistical testing. Secondary (and other exploratory) endpoints are considered as exploratory.

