6.1. How are the outcomes of this study defined?

The primary safety outcome is: All adverse events and serious adverse events collected from the start of study treatment until the end of the study and will be summarized for descriptive purposes.

The primary efficacy outcome is the time of loss of ambulation. Loss of ambulation is defined by the loss of walking with support.

The secondary efficacy outcomes are overall survival, HUI attributes and multiscores. Scores on the Vineland, GMFCS-MLD, ELFC-MLD, GMFM, LIPS, GMFCS, MACS CFCS and EDACS will be considered for descriptive purposes.

Other secondary outcomes are Guanabenz PK/PD parameters in plasma and will be summarized for descriptive purposes. Guanabenz exposure will also be correlated with clinical outcome measures.

For more information, please refer to pages 28 to 32 of the study protocol

6.2. Will any calculations or transformations be used to derive any outcome from the original data?

Disease duration will be calculated from age of onset until date of inclusion, screening, baseline, first day of dosing, end of titration, and visits. Ages will be calculated from the date of birth until date of inclusion, screening, baseline, first day of dosing, end of titration, and visits. Time to loss of walking, with or without support, will be calculated from the day of inclusion until the occurrence of the event.

HUI decision tables are used to generate HUI2 and HUI3 single-attribute utility scores, and applied coding algorithms to obtain overall HUI3 Health Index scores. Overall scores on the Vineland and LIPS will be calculated based on their respective domain scores.

6.3. What analysis method will be used and how will the treatment effects be presented?

For the primary efficacy outcome time to loss of ambulation, a comparison of the guanabenz-treated patients will be made with natural history data, adjusting for calendar year of symptoms onset.

For time to loss of ambulation, patients treated with Guanabenz will be matched to historical controls with a 1:2 matching ratio. The matching criteria are:

- Age of symptoms onset
- Degree of handicap regarding ambulation at comparable disease duration

Other variables might be added if considered crucial.

Primary analysis of the primary efficacy endpoint

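### At the one-sided 0.05 level of SAP section 4.1, an uncorrected McNemar test on 40 independent pairs has about 72–76% power, not the stated 80%, and the example does not describe the primary analysis

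*SAP*

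**What the plan says.** **Power example (section 3.3).** The sample size of 20 to 40 is set by feasibility, and the power calculation is introduced as an example. The endpoint is being alive and walking without support at 2 years. The setting is "Considering type I error equal to 0.1 and a McNemar test statistic". For the smaller case, "with 30 patients included within 3 years and 30 historical controls, the study has 80% power to declare guanabenz effective" if the proportion rises from 50% to 80.1%, 60% to 87.8% or 70% to 93.5%. For the larger case, "With 40 patients included in 2 years and 40 historical controls, the study has 80% power to declare guanabenz effective" at "from 50% to 75.5%, from 60% to 83.3%, or from 70% to 90.1" (per cent). The section adds that correlated data would raise the power, so the stated figures assume none. It also says that 1:1 matching might raise the power.

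**Significance level (section 4.1).** Efficacy outcomes are significant "if the one-sided p-values are less than 0.05".

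**Primary analysis (sections 6.1 and 6.3).** The outcome is time to loss of ambulation: "Loss of ambulation is defined by the loss of walking with support". For this analysis "patients treated with Guanabenz will be matched to historical controls with a 1:2 matching ratio". The methods are Kaplan-Meier, a log-rank test that allows for clustering, and a Cox model adjusted for calendar year of onset.

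**Timing (sections 1.4 and 3.6).** The final analysis comes about a year after the last enrolments, "as inclusion ended on May 31, 2024". Follow-up ends on 31 May 2025.

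**The concern.** There are two separate problems.

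1. **The stated power.** At the level the trial will use, the 40-pair rows fall short of 80%, while the 30-pair rows are right under one common version of the test. The two sets therefore do not appear to come from the same calculation.
2. **The link to the analysis.** Whatever its arithmetic, the example concerns a different event, a binary comparison at a fixed time and a different matching ratio.

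Section 3.3 words the claim as a property of the study. Readers of the results may therefore weigh a null or positive finding against an 80% figure that was never derived for the primary analysis.

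**Working it through.** **Inputs.** Pairs n, control proportion p1 and treated proportion p2 are from section 3.3. Within-pair correlation is 0, as section 3.3 implies. The critical value z = 1.645 follows from one-sided 0.05 in section 4.1; two-sided 0.10 gives the same value.

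**Formulas.** For independent pairs the discordant probabilities are b = p2(1 − p1) and c = p1(1 − p2), with ψ = b + c, δ = b − c and θ = b/ψ.

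- Asymptotic: power = Φ[(δ√n − z√ψ) / √(ψ − δ²)].
- Enumeration: sum over the number of discordant pairs m ~ Bin(n, ψ) and the number favouring treatment x ~ Bin(m, θ). The uncorrected test rejects if (2x − m)/√m ≥ z. The exact test rejects if P(X ≥ x) ≤ 0.05 for X ~ Bin(m, ½).

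**Asymptotic formula, 40 pairs.**

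- 50% to 75.5%: b = 0.3775, c = 0.1225, ψ = 0.5000, δ = 0.255. (1.613 − 1.163)/0.660 = 0.682, power 75.2%.
- 60% to 83.3%: b = 0.3332, c = 0.1002, ψ = 0.4334, δ = 0.233. (1.474 − 1.083)/0.616 = 0.635, power 73.7%.
- 70% to 90.1%: b = 0.2703, c = 0.0693, ψ = 0.3396, δ = 0.201. (1.271 − 0.959)/0.547 = 0.572, power 71.6%.

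**All six rows (power in %, stated 80 in each; the three figures are for p1 = 50, 60, 70%).**

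| Test | 30 pairs | 40 pairs |
|---|---|---|
| One-sided 0.05, uncorrected, enumerated | 79.5 / 81.0 / 79.6 | 76.3 / 75.3 / 74.4 |
| One-sided 0.05, second-order formula | 79.7 / 80.8 / 79.1 | 76.5 / 75.3 / 73.8 |
| One-sided 0.05, asymptotic formula | 77.6 / 77.8 / 74.8 | 75.2 / 73.7 / 71.6 |
| One-sided 0.05, exact | 71.7 / 71.1 / 65.6 | 69.8 / 68.0 / 64.4 |
| One-sided 0.10, asymptotic formula | 87.7 / 87.8 / 85.7 | 85.8 / 84.7 / 83.1 |
| One-sided 0.10, exact | 82.4 / 82.8 / 79.7 | 80.8 / 79.1 / 77.0 |

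A continuity-corrected test, enumerated, gives the same figures as the exact test in both settings.

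The plan's 30-pair figures therefore reproduce at the section 4.1 level, by enumeration or the second-order formula. Its 40-pair figures do not reproduce under any variant at that level. The only McNemar variant found within about 3 points of 80% in all six rows is the exact (or continuity-corrected) test at one-sided 0.10, which is twice the alpha of section 4.1.

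**What would give 80% at one-sided 0.05.** With 40 pairs and the uncorrected test by enumeration, the treated proportions are 76.7, 84.6 and 91.3%, against the stated 75.5, 83.3 and 90.1%. At the stated proportions, the pairs needed are 45/46/47 (enumeration), 46/48/50 (asymptotic) or 51/53/56 (exact).

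**Example against primary analysis.**

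| | Section 3.3 | Sections 6.1 and 6.3 |
|---|---|---|
| Event | not alive and walking without support | loss of walking with support |
| Outcome type | binary at 2 years | time to event |
| Ratio | 1:1 | 1:2 |
| Test | McNemar | clustered log-rank, then Cox |

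The remark on 1:1 matching does not fit, because the example already has equal numbers of patients and controls. For a fixed number of treated patients, more controls raise power. An unpaired two-proportion approximation with two controls per patient gives 86.7/85.2/82.9% at the stated 40-patient effects.

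**Follow-up.** Anyone enrolled after 31 May 2023 has less than 2 years by 31 May 2025, and the last entrants have about 1 year. They could not supply the example's 2-year outcome.

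**The case against.** **The literal reading.** Section 3.3 says 0.1 without sidedness. If one-sided 0.10 was meant, the exact test needs 75.2/83.6/90.8% for 80% power with 40 pairs, within 1 point of the stated figures. The fault may then be an unstated alpha that differs from section 4.1, not faulty arithmetic. This stands as a possible explanation, but it leaves the example at twice the trial's alpha and still does not match every row.

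**Correlation.** A within-pair correlation of 0.1 brings the uncorrected test on 40 pairs to 80.3/79.3/78.6%. It also lifts the 30-pair rows to 83.5/84.9/82.9%, and section 3.3 treats correlation as a gain on top of 80%.

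**Small stakes.** The shift in the detectable proportion is only about 1.2 points, the calculation is labelled an example, and enrolment is over. All true, and the reason the severity is modest.

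**Stronger readings that the SAP does not support.**

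- *A reader might infer that the primary analysis has less than 80% power.* This is not shown. As an illustration, take the stated proportions as 2-year event-free rates with exponential times. The hazard ratios are then ln(p2)/ln(p1) = 0.32/0.25/0.19 for 30 patients and 0.41/0.36/0.29 for 40. With 1:2 matching, follow-up spread evenly over 1 to 4 years, 8% yearly dropout (assumed) and one-sided 0.05, the Schoenfeld formula gives about 95–98% and 92–94%. It is only approximate at such extreme ratios. If loss of walking with support is much rarer than the example's event, power would be lower. The SAP gives no rate for it.
- *A reader might discount the power for patients who cannot reach 2 years.* The planned analysis keeps them as censored. The 40-patient row also assumes accrual in 2 years, which from the expected start of 31 May 2021 would give everyone 2 years.
- *A reader might object that children who enter walking with one-hand support fail the example's endpoint at the start.* That is a further difference from the primary endpoint, but no error in the 50–70% control rate, which is stated for the eligible population.

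**Conclusion.** The point holds in a limited form. At one-sided 0.05 with independent pairs, 40 pairs give 74–76% (uncorrected, enumerated), 72–75% (asymptotic) or 64–70% (exact) where section 3.3 states 80%. The shortfall is about 4 to 6 points under the version that reproduces the 30-pair rows. The size rests on reading the example at the section 4.1 level, a reading which the 30-pair match supports, and on zero correlation.

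Separately, and without any calculation, the example does not describe the primary analysis in event, outcome type, test or matching ratio. The power of the planned analysis is therefore not established; it may lie above or below 80%. No sample size, test or decision threshold is affected.

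**What to change.** In section 3.3:

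1. State whether 0.1 is one- or two-sided and which McNemar variant was used, and align the level with section 4.1.
2. At one-sided 0.05 with the uncorrected test, restate the 40-pair alternatives as about 76.7, 84.6 and 91.3%, or keep the stated alternatives and give the power as about 74–76%.
3. Say that the figures are illustrative and apply neither to the primary endpoint nor to its analysis, and that the last entrants cannot supply a 2-year outcome. Remove or reword the remark on 1:1 matching.
4. Preferably, add the detectable hazard ratio for the planned 1:2 time-to-event analysis at one-sided 0.05. Use the number actually enrolled and the actual follow-up, over a stated range of control rates for loss of walking with support.

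The cost is wording and a short calculation. Enrolment has closed, so the actual number can be used, and no patients or data are added. The corrected 40-pair figures will look slightly less favourable.

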3.4. What is the hypothesis testing framework for this study?

The guanabenz trial uses a superiority hypothesis testing framework for all primary, secondary and exploratory efficacy outcomes.

3.5. Will interim analyses be performed in this study?

No interim analyses are planned.

3.6. When will the final statistical analysis of the study data be performed?

The statistical analysis of the primary and secondary endpoints assessed during the hospital stay will be conducted after the last patient has been discharged and the database has been closed (scheduled for July 16, 2025). This will occur approximately one year after the final participants were enrolled, as inclusion ended on May 31, 2024. The current estimate is that these statistical analyses will be performed in August and September 2025.

3.7. At which time points are the outcomes measured and which "windows" are allowed?

The time points of the visits are presented in Table 3 on page 71 of the protocol. As stated on page 71, all visits have a visit window of 14 days before and after the nominal time points, except for visits M0, M12, M24, M36, M48, which have a visit window of 28 days before and after the nominal time points. As indicated on page 71, the end of study visit has to be in the last 6 months before the end of study on May 31, 2025.

Section 4. Statistical Principles.

4.1. Which level or levels of statistical significance will be used in the study?

Primary and secondary efficacy outcomes will be considered significantly different between guanabenz treated participants and historical controls if the one-sided p-values are less than 0.05.

4.2. Will the analysis adjust for multiplicity of statistical testing to ensure control of type I error rate?

As there is one primary efficacy endpoint (loss of ambulation), the analysis will not adjust for multiplicity of statistical testing. Secondary (and other exploratory) endpoints are considered as exploratory.

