4.3. Which confidence intervals will be reported?

Two-sided 95% confidence intervals will be presented for all efficacy parameters.

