In the primary analysis, treated patients will be compared to their matched historical controls. We will analyze time to loss of ambulation using the Kaplan-Meier method and the log-rank test, considering the presence of clustered data. Next, the Cox proportional hazards model will be used to provide an estimate of the effect size, which will contain treatment and will be adjusted for calendar year of symptoms onset. The effects size will be reported using the Hazard Ratio (HR). We will take matching into account when estimating standard errors.

Secondary analysis of the primary efficacy endpoint

In the secondary analysis, we will use historical controls with different matching procedures and different matching ratios. We will use the Kaplan-Meier method and the log-rank test, considering the presence of clustered data. The Cox model will contain treatment and will be adjusted for calendar year of symptoms onset, reporting the effects size using the Hazard Ratio (HR).

Analysis of secondary efficacy endpoints.

The same methods that we used for the primary analysis will be used for overall survival. The HUI scores will be analyzed using linear mixed models adjusting for treatment and calendar year of age of onset. A population pharmacokinetic model will be used to assess the drug exposure (such as AUC or concentration at steady state) and this will then be used to assess the relationship with clinical outcomes using correlation or regression methods.

Descriptive analysis for primary and secondary safety endpoints

A listing of all adverse and serious adverse events will be presented for the guanabenz-treated participants, including the corresponding date and time of collection.

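### The significance rule in SAP 4.1 covers secondary outcomes that 4.2 calls exploratory and leaves unadjusted, and its one-sided 5% level does not match the 95% interval in 4.3

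*SAP*

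**What the plan says.** Five places in the SAP bear on this point.

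- **Section 4.1** sets the decision rule and its scope: primary and secondary efficacy outcomes "will be considered significantly different between guanabenz treated participants and historical controls if the one-sided p-values are less than 0.05".
- **Section 4.2** explains why nothing is adjusted: "As there is one primary efficacy endpoint (loss of ambulation), the analysis will not adjust for multiplicity of statistical testing". It then adds: "Secondary (and other exploratory) endpoints are considered as exploratory".
- **Section 4.3** fixes the interval: "Two-sided 95% confidence intervals will be presented for all efficacy parameters".
- **Section 3.4** states that the trial "uses a superiority hypothesis testing framework for all primary, secondary and exploratory efficacy outcomes".
- **Section 3.3** gives the level in its power example: "Considering type I error equal to 0.1 and a McNemar test statistic, with 30 patients included within 3 years and 30 historical controls". It does not say whether 0.1 is one-sided or two-sided.

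Section 6.1 lists the secondary efficacy outcomes as overall survival and the HUI attributes and multi-scores. Section 6.3 names two procedures for the primary endpoint: a log-rank test that allows for clustering, and a Cox model adjusted for calendar year of onset that supplies the hazard ratio. The SAP does not say which p-value the rule in 4.1 refers to, does not mention a 90% interval, and does not say how to read a result on which test and interval disagree.

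**The concern.** There are two separate problems.

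The first is scope. If secondary outcomes are exploratory, they should not carry a prespecified declaration of significance. If they do carry one, a single primary endpoint no longer justifies leaving the tests unadjusted. Section 4.1 takes one position and 4.2 the other. A later report could cite 4.1 for a claim on survival or on one HUI attribute and cite 4.2 for having adjusted nothing. Section 6.6 widens the field by repeating all primary and secondary efficacy outcomes in two age-at-onset groups.

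The second is the pairing of test and interval. The two use different critical values, so a primary result can pass the test while its published interval includes no effect. The trial is open-label and historically controlled, with 20 to 40 treated patients, so readers will lean heavily on the hazard ratio and its interval. A borderline result is realistic, and deciding which measure governs after seeing the data would be post hoc.

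**Working it through.** **The plan's own figure.** Section 3.3 states 80% power at type I error 0.1 with a McNemar test in six scenarios. Assume independent pairs, with d = p2 − p1 and ψ = p1(1 − p2) + p2(1 − p1). Miettinen's approximation is

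power = Φ{ [d√(nψ) − zψ] / √[ψ² − d²(3 + ψ)/4] }.

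For 30 pairs, 50% to 80.1%, z = 1.645: d = 0.301 and ψ = 0.5, so (1.166 − 0.823)/0.413 = 0.831 and power is 79.7%.

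| Pairs | Scenario | z = 1.645 | z = 1.960 |
|---|---|---|---|
| 30 | 50% to 80.1% | 79.7% | 67.4% |
| 30 | 60% to 87.8% | 80.8% | 68.2% |
| 30 | 70% to 93.5% | 79.1% | 65.2% |
| 40 | 50% to 75.5% | 76.5% | 64.2% |
| 40 | 60% to 83.3% | 75.3% | 62.6% |
| 40 | 70% to 90.1% | 73.8% | 60.4% |

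The 30-pair rows reproduce when 0.1 is read as two-sided, which is the same as one-sided 0.05. The 40-pair rows do not, and no variant tried reproduced all six. That is a separate matter. What counts here is that, on this reading, 3.3 agrees with the level in 4.1.

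**Secondary outcomes.** For k independent tests at 0.05 with no true effect, P(at least one false positive) = 1 − 0.95^k. The SAP does not count the secondary tests, so k is an assumption.

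- k = 2: 1 − 0.9025 = 9.8%
- k = 3: 14.3%
- k = 10: 40.1%

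Positive correlation among the outcomes lowers these figures.

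**Test against interval.** One-sided p < 0.05 needs z > 1.645. A two-sided 95% interval excludes no effect in the favourable direction only if z > 1.960, which is one-sided p < 0.025. A two-sided 90% interval uses 1.645. If one statistic Z drives both test and interval, the zone of disagreement is 1.645 < Z < 1.960.

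- No effect: 0.05 − 0.025 = 2.5%.
- Effect with 80% power at one-sided 0.05: Z has mean 1.645 + 0.842 = 2.487, so the probability is Φ(0.842) − Φ(0.527) = 0.800 − 0.701 = 9.9%.

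**Illustration on the hazard-ratio scale.** The SAP gives no event count, so D = 20 and D = 40 are assumed. With the 1:2 matching of 6.3, SE(log HR) = 1/√(D × 1/3 × 2/3), ignoring clustering and covariate adjustment. Take one-sided p = 0.04 (z = 1.751).

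| D | SE | HR | 95% interval | 90% interval |
|---|---|---|---|---|
| 40 | 0.335 | 0.556 | 0.288 to 1.073 | 0.320 to 0.965 |
| 20 | 0.474 | 0.436 | 0.172 to 1.104 | 0.200 to 0.951 |

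In both rows the result is significant under 4.1, the 95% interval includes 1 and the 90% interval does not.

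**The case against.** The strongest reply is that nothing here is a contradiction. Section 4.1 gives the only decision rule, and 4.3 says only that intervals will be presented, with no decision role. A 95% interval beside a one-sided test is common, and it shows the reader more uncertainty than the test does. One-sided 0.05 is disclosed and fits the 0.1 in 3.3 if that is two-sided. On secondary outcomes, 4.2 follows 4.1 directly and can be read as qualifying it: a nominal threshold first, its evidential status second.

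Much of this stands. A reader might infer that one-sided 0.05 is itself an error, or that 4.1 and 4.3 cannot both be followed. The SAP supports neither inference. The 2.5% under no effect is part of the 5% that the plan openly accepts and is not extra error.

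A reader might also infer that every one-sided p between 0.025 and 0.05 must come with a 95% interval covering 1. That is exact only when test and interval share one statistic. If the log-rank p-value decides and the adjusted Cox model gives the interval, the two can differ in either direction, and even a 90% interval need not agree with the test.

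What does not stand is the claim that 4.2 settles the scope of 4.1. The rule in 4.1 names secondary outcomes and attaches a declaration of significance to them. Nothing in 4.2 withdraws that declaration or calls the p-values nominal.

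**Conclusion.** The point holds in two limited parts.

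1. The scope of 4.1 conflicts with the exploratory status in 4.2. This part matters more, because it changes what may be concluded about survival and HUI. It rests on the wording alone. The error rates of 9.8% to about 40% illustrate it under independence and assumed counts. It would be tempting to quote 40% as this trial's error rate, but the SAP gives no count of ten, and HUI attributes and multi-scores come from one instrument and are unlikely to be independent.

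2. The interval in 4.3 does not correspond to the test level in 4.1. For a shared statistic the zone of disagreement is one-sided p from 0.025 to 0.05, entered with probability about 10% at an effect with 80% power. With different procedures for test and interval the figure is approximate. This is a reporting gap that leaves the decision rule valid, but it should be closed before the results are seen.

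**What to change.** - In 4.1, limit the significance rule to the primary efficacy endpoint. Report secondary outcomes as estimates with intervals, label any p-values nominal, and align 3.4 with this.
- Keep one-sided 0.05 for the primary endpoint, and state whether the clustered log-rank test or the Cox model supplies the deciding p-value.
- In 4.3, add the two-sided 90% interval for the primary hazard ratio beside the 95% interval, and say that the 90% interval corresponds to the test level.

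The cost is a few sentences, one extra interval, and giving up confirmatory wording for secondary outcomes. The level and power of the primary test do not change.

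Moving to one-sided 0.025 would also align test and interval, but it is not part of this fix. In the scenarios of 3.3 it would lower power to about 60% to 68% (last column of the power table), and with 40 assumed events at 1:2 it would move the critical hazard ratio from exp(−1.645 × 0.335) = 0.576 to exp(−1.960 × 0.335) = 0.518.
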